9.1 Data Management Procedures

1. Investigators must ensure data are truthful, complete, and accurate.
2. Any correction to study records must be made by a single line through the original entry, with the corrected data annotated, the reason documented, and the investigator's signature and date provided; erasing or overwriting original records is not permitted.
3. Required laboratory examination items should be complete as applicable in routine care.

9.2 Data Recording and Document Retention

Participant data in case report forms will be recorded using coded identifiers; participants may only be identifiable via the participant code or initials.

This study will use an Excel database for data management, with double data

entry. After source data verification and confirmation of data integrity, the database will be locked. After database lock, the analysis dataset will be exported for statistical analysis. Locked data cannot be edited. If issues are identified after database lock, they may be corrected within the statistical analysis program after confirmation.

10. Statistical Analysis

10.1 Sample Size Determination

This is a single-center, retrospective, observational study. One-way analysis of variance (ANOVA) will be used to explore factors associated with concordance versus non-concordance between EUS diagnosis and pathological diagnosis. Using G*Power (version 3.1.9.7) with an effect size of 0.25, $\alpha = 0.05$, power $(1-\beta) = 0.80$, 10 predictors, and 2 groups, the required sample size was calculated to be 269 cases.

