**Study on the Diagnostic Accuracy of Endoscopic Ultrasound for Colorectal
Subepithelial Lesions**

NCT number: not yet assigned

Document date: 2023.11.20

1. Background

On endoscopic ultrasound (EUS), the normal intestinal wall is typically visualized as a five-layer structure with alternating hyperechoic and hypoechoic layers, corresponding to the superficial mucosal interface, deep mucosa/muscularis mucosa, submucosa, muscularis propria, and serosa. For subepithelial lesions (SELs), EUS can measure lesion size and assess sonographic features such as margins, homogeneity, and acoustic shadowing. It also provides information on the layer of origin, lesion location, and relationship to surrounding tissues. By integrating these findings, EUS may help predict pathological nature and guide subsequent management.

However, compared with final histopathology, the reported diagnostic accuracy of EUS for gastrointestinal SELs is approximately 43%–79%, which may not fully meet current clinical needs.

2. Objectives

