3.1 Primary Endpoint

Coincidence rate between EUS diagnosis and pathological diagnosis.

4. Study Design

This is a single-center, retrospective, observational study. All patients who underwent colorectal EUS at Shenzhen Hospital of Southern Medical University between 2015 and 2023 will be screened, and their endoscopy/EUS reports and pathology reports will be retrospectively reviewed and analyzed.

If a patient had two or more colorectal lesions evaluated by EUS, lesions at different sites will be treated as independent EUS examinations. Only SEL cases with histopathologic confirmation will be included for further analysis.

During the study, no randomization will be performed and no protocol-driven treatment will be administered or provided. When clinically indicated, treatment decisions and treatment selection will be made at the discretion of the treating physician.

5. Study Population

The study population consists of patients with colorectal subepithelial lesions.

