6.4 Data Collection Items

1. Demographics: age, sex, initials;
2. Lesion location and size (maximum diameter);
3. EUS echogenic features, layer-related characteristics, EUS diagnosis (primary diagnosis), operator, and device information;
4. Pathology acquisition method, pathological layer, and pathological diagnosis.

7. Criteria for Study Termination / Suspension

7.1 The sponsor has the right to terminate or suspend the study. Before termination/suspension, the sponsor must notify the investigator, the ethics committee, and relevant regulatory authorities and provide the rationale. If the study is terminated/suspended early, restarting the study requires ethics committee approval.

7.2 Termination or suspension as required by the ethics committee.

8. Study Completion

The study will be completed when data collection reaches the predefined time interval.

9. Data Management

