10.3 Statistical Software and General Requirements

- Statistical analyses will be performed using SPSS.
- Continuous variables will be summarized using mean, standard deviation, median, minimum, and maximum values.
- Categorical variables will be summarized using frequencies and percentages.
- One-way ANOVA will be used to evaluate differences in potential factors between the concordant and non-concordant groups.
- Multivariable logistic regression will be performed to identify key factors independently associated with diagnostic concordance.

11. Study Management

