11.3 Problems During the Study and Corrective Measures

1. Protocol amendments: After ethics approval, any revision requires a “protocol amendment statement” signed by the PI. Amendments may be made only after consultation and agreement between the investigators and the sponsor (and/or the registration applicant, as applicable).
2. After revision, the amended protocol must be submitted to the ethics committee for review and approval prior to implementation.
3. No study personnel may deviate from the protocol.

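### The 269 cases in section 10.1 do not belong to the two-group one-way ANOVA named there, which needs 128 with equal groups; 269 fits an unplanned F test with 10 numerator df and does not size the logistic model.

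*Combined protocol and SAP*

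**What the plan says.** Section 10.1 names one-way ANOVA as the method for exploring factors associated with concordance. It gives G*Power 3.1.9.7 as the software and lists effect size 0.25, alpha 0.05 and power 0.80, then: "10 predictors, and 2 groups, the required sample size was calculated to be 269 cases". It does not name the G*Power procedure, the scale of the effect size, or the expected split between the groups.

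Section 10.3 confirms which groups are meant: "One-way ANOVA will be used to evaluate differences in potential factors between the concordant and non-concordant groups". It then adds a second analysis: "Multivariable logistic regression will be performed to identify key factors independently associated with diagnostic concordance". Section 10.1 does not mention that model.

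The sample itself is set elsewhere. Section 4 screens every patient who had colorectal endoscopic ultrasound (EUS) at the centre between 2015 and 2023 and restricts the analysis: "Only SEL cases with histopathologic confirmation will be included for further analysis". Where a patient has several lesions, "lesions at different sites will be treated as independent EUS examinations". Section 8 says: "The study will be completed when data collection reaches the predefined time interval".

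**The concern.** The inputs in section 10.1 do not describe one test. A one-way ANOVA with two groups has one numerator df and has no place for predictors, so a count of 10 predictors cannot enter its sample size. If it did enter, the reported figure answers a different question from the one the section poses.

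Two things are at stake. This is the only sample-size statement in the plan, and it should be reproducible from the test it names. Also, quoting 10 predictors beside 80% power invites the reader to think that the multivariable model has been sized. That model is the only planned analysis of independent association, and so it bears directly on the primary objective in section 2.1.

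**Working it through.** **Inputs.** From section 10.1: effect size 0.25, alpha 0.05, power 0.80, 10 predictors, 2 groups, N = 269. Assumption: 0.25 is Cohen's f, the scale G*Power uses for ANOVA. With two equal groups, f = 0.25 is the same as d = 0.5. The concordance range of 43% to 79% comes from section 1. It refers to gastrointestinal lesions generally and is not used in section 10.1.

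**Formula.** Power is the probability that a noncentral F variable, with numerator df1, denominator df2 and noncentrality λ = N·f², exceeds the central F critical value at alpha 0.05. With f = 0.25, λ = 0.0625·N.

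**1. Reproducing 269.** Take df1 = 10 and df2 = N − 2.
- N = 269: λ = 0.0625 × 269 = 16.81, power 0.8003.
- N = 268: power 0.7984.
- So 269 is the smallest N that reaches 0.80.
- With the same df2, df1 = 9 gives 259 and df1 = 11 gives 279.

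The numerator df is therefore identifiable as 10. The denominator df is less so: small changes to it still give 269, while df2 = N − 11 (a linear regression on 10 predictors with f² = 0.0625) gives 270.

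**2. The test that is named.** Take df1 = 1 and df2 = N − 2, with equal groups.
- N = 128: λ = 0.0625 × 128 = 8.00, power 0.8015.
- N = 127: power 0.7983.
- So the requirement is 128, or 64 per group.
- At N = 269: λ = 16.81, power 0.983.

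**3. Other readings that might rescue 269.**
- Two groups with 10 covariates (df1 = 1, df2 = N − 12): 128.
- Bonferroni alpha of 0.05/10 = 0.005 for two groups: 217.
- Inflating 128 for 10% to 20% dropout: 128/0.9 = 142.2, so 143; 128/0.8 = 160.
- Reading 0.25 as d: 505. Reading it as f² with 10 predictors: 75.

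None of these gives 269.

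**4. Unequal groups.** The formula in f alone gives 128 whatever the split. To see what an uneven split does, hold the difference in means at d = 0.5 and let a proportion p be concordant. Then λ = d²·N·p(1 − p) = 0.25·N·p(1 − p).

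| Concordant | N needed | λ at N = 269 | Power at N = 269 |
|---|---|---|---|
| 43% | 131 | 0.25 × 269 × 0.2451 = 16.48 | 0.98 |
| 50% | 128 | 0.25 × 269 × 0.2500 = 16.81 | 0.98 |
| 79% | 192 | 0.25 × 269 × 0.1659 = 11.16 | 0.91 |
| 85% | 249 | 0.25 × 269 × 0.1275 = 8.57 | 0.83 |
| 90% | 351 | 0.25 × 269 × 0.0900 = 6.05 | 0.69 |

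So 269 covers the named ANOVA across the cited range of 43% to 79%, and stops doing so between 85% and 90%.

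**5. The logistic model.** No sample size can be computed for it. The plan gives no odds ratio, no expected concordance for these lesions and no number of fitted parameters, and f = 0.25 is not an effect size for a logistic regression.

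**The case against.** The strongest reply is that nothing depends on 269. The study is retrospective and takes all eligible records in a fixed period, so there is no recruitment target or stopping rule to go wrong, and 269 is more than the named test needs across the cited concordance range. This stands, and it limits the weight of the point. It does not make the stated requirement correct.

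A second reply is that the listed inputs, taken together, do reproduce 269, so the fault is a mislabelled test and not a slip in arithmetic. That is fair as a description: the calculation appears sound for a test that the plan does not contain. The effect-size scale and the G*Power procedure are both unstated, so the route to 269 remains an inference.

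A third is that 128 describes only part of the planned work. A comparison of means suits continuous factors. Among the items in section 6.4, age and maximum diameter are clearly continuous; sex, location, operator and others are categorical or likely to be so. This also stands, and any statement of 128 needs that condition attached.

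Three stronger readings are tempting, and the documents support none of them. A reader might infer that the study is too small for its ANOVA; the table above shows otherwise within the cited range. A reader might infer that 269 is always on the safe side; that fails for a very uneven split, and the cited range is not specific to colorectal lesions. A reader might infer that the logistic model is underpowered; the plan gives no basis to say so, only no basis to say that it is adequately sized.

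**Conclusion.** The point holds as a mismatch between the named test and the reported figure. With 0.25 read as Cohen's f, the two-group ANOVA needs 128 with equal groups, against the stated 269, a difference of 141 cases. The figure 269 corresponds to 10 numerator df, and no 10-df F test appears in the plan. The excess is conservative for the ANOVA between 43% and 79% concordance (power 0.98 falling to 0.91 at d = 0.5), but not at every split (0.69 at 90%). The logistic regression has no sizing of its own. The justification should be corrected, but the consequence is modest, because the available records determine how many lesions are analysed.

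**What to change.** In section 10.1, stop presenting 269 as the required size. Describe the sample as all eligible, histologically confirmed lesions from 2015 to 2023, in line with sections 4 and 8.

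If the ANOVA calculation is kept, name the G*Power procedure, state that 0.25 is Cohen's f, and give 1 numerator df and N = 128 for a continuous factor with equal groups, noting that more are needed with unequal groups when d is fixed at 0.5. Present this as a description of that test. It should not become a new target or a reason to analyse fewer lesions. Add one sentence saying that neither 269 nor 128 sizes the logistic model in section 10.3.

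The cost is a rewording, with no more patients or data. If ethics approval has already been given, section 11.3 requires an amendment statement signed by the principal investigator, and "the amended protocol must be submitted to the ethics committee for review and approval prior to implementation". Section 11.4.3 schedules data collection for October 2023 to January 2024, so the change may come after collection has begun. The other cost is that the stated justification will look less favourable, since it will no longer appear to support a 10-predictor analysis.

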10.2 Statistical Methods

Analyses will include case distribution, demographic characteristics and baseline analyses, and outcome analyses.

10.3 Statistical Software and General Requirements

- Statistical analyses will be performed using SPSS.
- Continuous variables will be summarized using mean, standard deviation, median, minimum, and maximum values.
- Categorical variables will be summarized using frequencies and percentages.
- One-way ANOVA will be used to evaluate differences in potential factors between the concordant and non-concordant groups.
- Multivariable logistic regression will be performed to identify key factors independently associated with diagnostic concordance.

11. Study Management

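### One-way ANOVA is the only univariable test named, so for unordered factors with three or more levels the p-value depends on how the levels are numbered

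*Combined protocol and SAP*

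**What the plan says.** Section 10.3 gives the univariable analysis in one sentence: "One-way ANOVA will be used to evaluate differences in potential factors between the concordant and non-concordant groups". Section 10.1 says the same: "One-way analysis of variance (ANOVA) will be used to explore factors associated with concordance versus non-concordance between EUS diagnosis and pathological diagnosis". It then gives the size calculation, "with an effect size of 0.25", alpha 0.05 and power 0.80, ending with "10 predictors, and 2 groups, the required sample size was calculated to be 269 cases". In both places the two groups are concordant and non-concordant lesions, and each candidate factor is the variable compared.

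Section 10.3 describes categorical variables by counts and percents but names no test for them. Section 10.2 adds none.

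Section 6.4 lists the candidate data. Age and maximum diameter are clearly continuous. The rest are wholly or mostly categorical: sex, location, the EUS items ("EUS echogenic features, layer-related characteristics, EUS diagnosis (primary diagnosis), operator, and device information"), and the pathology items (acquisition method, layer and diagnosis). The number of levels is not given for any of them.

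The multivariable step is also one sentence: "Multivariable logistic regression will be performed to identify key factors independently associated with diagnostic concordance". The plan does not say how categorical factors are coded or which factors enter the model.

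**The concern.** One-way ANOVA between two groups compares two means. For age or diameter the mean is meaningful. For an unordered factor such as EUS diagnosis, location or operator, the mean is that of whatever integers label the levels. With three or more levels, different numberings give different means, different F statistics and different p-values from identical data.

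The primary objective in section 2.1 is to find which factors go with agreement between EUS and pathology. Under the plan as written, whether a real unordered factor is reported at the univariable step can turn on a data-entry convention. If ANOVA results also decide which factors reach the logistic model, or if the model takes the same numeric codes, the fault carries through to the main conclusion.

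**Working it through.** **Inputs.** From section 10.1: N = 269, effect size 0.25 (read as Cohen's f), alpha 0.05, power 0.80, 10 predictors, 2 groups. From section 10.3: the ANOVA sentence. Level counts, level sizes and concordance rates by level are not in the documents. All tables below are assumptions, with near-equal level sizes that sum to 269.

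**1. The plan's own figure.** The power of an F-test uses noncentrality λ = f² × N.
- With 10 numerator df and 2 groups: λ = 0.0625 × 269 = 16.81, df = 10 and 267, power 0.8003. At N = 268 power is 0.7984. So 269 reproduces.
- For the two-group one-way ANOVA that the text names (1 numerator df): λ = 0.0625 × 128 = 8.0, df = 1 and 126, power 0.8015. At N = 127 power is 0.7983. That test needs 128.

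The stated 269 therefore belongs to a 10-df F-test, not to the test named beside it.

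**2. Mild three-level example.** Levels A, B and C hold 90, 90 and 89 lesions, of which 68, 50 and 58 are concordant (76%, 56%, 65%). Totals: 176 concordant and 93 non-concordant.

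*Chi-square* = Σ nᵢ(pᵢ − p)² / [p(1 − p)], with p = 176/269 = 0.6543 and p(1 − p) = 0.2262. The sum is 0.923 + 0.877 + 0.001 = 1.801, and 1.801/0.2262 = 7.96 on 2 df, **p = 0.0187**. Relabelling does not change it.

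*ANOVA on codes*: F = (difference in mean code)² / [(1/176 + 1/93) × within-group mean square].

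| Codes for A, B, C | Mean, concordant | Mean, non-concordant | F (1, 267 df) | p |
|---|---|---|---|---|
| 1, 2, 3 | 342/176 = 1.943 | 195/93 = 2.097 | 2.16 | 0.143 |
| 1, 3, 2 | 334/176 = 1.898 | 204/93 = 2.194 | 8.14 | 0.0047 |
| 2, 1, 3 | 360/176 = 2.045 | 177/93 = 1.903 | 1.85 | 0.175 |

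Each row has a mirror-image numbering with the same p, so 4 of 6 numberings (2 of 3 distinct ones) miss 0.05.

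**3. Less favourable four-level example.** Levels of 68, 67, 67 and 67, with 54, 33, 53 and 34 concordant (79/49/79/51%). Chi-square = 25.24 on 3 df, p = 0.000014. ANOVA p runs from 0.0000036 to 0.997; 8 of 24 numberings miss 0.05.

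**4. Power** (20,000 simulations per scenario, N = 269).

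| True concordance by level | Chi-square | ANOVA on codes, by numbering |
|---|---|---|
| 75/55/65% | 0.72 | 0.28, 0.30 or 0.81 |
| 60/80/60% | 0.87 | 0.06 to 0.83 |
| 75/55/75/55% | 0.84 | 0.03 to 0.88 |
| 65% in all four levels (no effect) | 0.050 | 0.048 to 0.053 |

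The last row shows that type I error is not inflated.

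**5. Where the problem does not arise.** With two levels (101/135 versus 80/134 concordant), ANOVA gives p = 0.0081 and chi-square 0.0083. Layer coded by depth is ordered, so numeric codes are defensible there.

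**6. The logistic model.** On the three-level table, logistic regression on the numeric code gives p = 0.0046, 0.141 or 0.173 by numbering, the same fault as ANOVA. With indicator variables the likelihood-ratio p is 0.018 under any numbering. On the four-level table the numeric code gives p from 0.0000039 to 0.997; indicators give 25.80 on 3 df, p = 0.000011.

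**The case against.** The strongest reply is that ANOVA could be run the other way round, with factor levels as the groups and 0/1 concordance as the outcome. Numbering then has no effect: p = 0.018 on the three-level table and 0.0000089 on the four-level table, both close to chi-square. This is correct as statistics, but section 10.3 compares factors between concordance groups and section 10.1 specifies two groups. At best the plan is ambiguous, and it would still need to say which analysis is meant.

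A second reply is that the harm is conditional. The plan never says that nominal factors will be averaged as codes; that is what the ANOVA sentence implies when taken literally. Section 10.1 calls the ANOVA step exploratory, and section 10.3 gives the independent-factor conclusion to logistic regression. Nothing says that ANOVA screens entry or that codes enter as numbers. This stands as a limit on the harm: if the model uses indicators and does not depend on ANOVA for entry, the damage is confined to the univariable results. The plan gives neither assurance.

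Third, the size is shown only on assumed tables. The four-level pattern is close to a worst case, and in the mild case one numbering gives ANOVA more power than chi-square (81% against 72%). That is fair. Dependence on numbering follows from the algebra; how much it matters here cannot be known from the documents.

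**Conclusion.** The concern holds and should be fixed. As worded, sections 10.1 and 10.3 apply a comparison of means to factors that have no meaningful mean, and name no alternative. For unordered factors with three or more levels the univariable p-value is arbitrary. In the mild assumed case it ranges from 0.005 to 0.18 against a fixed 0.019, and power falls from 72% to about 30% under two of the three distinct numberings. Type I error is intact, and continuous factors, two-level factors and depth-ordered layer are not affected. The size rests on assumed level counts, rates and level sizes. The reach into the final conclusion depends on coding and entry rules that the plan leaves open. The 269 is arithmetically reproducible but belongs to a different test from the one named.

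**What to change.** **Section 10.3.**
- Test categorical factors with Pearson chi-square, or Fisher's exact test when expected counts are small. A trend or rank test may be added for depth-ordered layer.
- Keep the t-test/ANOVA, or Mann-Whitney, for age and maximum diameter.
- In the logistic model, enter each unordered factor as indicator variables with one joint likelihood-ratio test, and state that ANOVA p-values do not decide entry.

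**Section 10.1.** Align the ANOVA sentence with 10.3 and say which test the 269 refers to. If the basis becomes chi-square, 269 lesions give 80% power at w = 0.17, 0.19 and 0.20 for factors with 2, 3 and 4 levels (1, 2 and 3 df).

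**Cost.** A few sentences and a restated sample-size justification; no new data. Indicator coding uses more degrees of freedom, so sparse levels, such as low-volume operators, may need a grouping stated in advance. For a truly ordered factor chi-square gives up a little power (92% against 98% with ordered codes at assumed rates of 80/70/60/50%), which is why the trend option is offered for layer.

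### For age and maximum diameter, ordinary one-way ANOVA assumes equal variances in two groups whose sizes the outcome sets; naming Welch's test in 10.3 protects the 5% level at almost no cost.

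*Combined protocol and SAP*

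**What the plan says.** Section 10.3 names one method for comparing factors between the two outcome groups: "One-way ANOVA will be used to evaluate differences in potential factors between the concordant and non-concordant groups". Section 10.1 names the same method: "One-way analysis of variance (ANOVA) will be used to explore factors associated with concordance versus non-concordance between EUS diagnosis and pathological diagnosis". Neither section mentions a check of variances, an unequal-variance version, a transformation or a rank-based alternative. Section 10.2 lists only the broad blocks of analysis.

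Section 6.4 collects two factors that are naturally continuous: age, and the diameter in "Lesion location and size (maximum diameter". No SD is given for either, overall or by group.

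No split between concordant and non-concordant lesions is planned. The only guide is in the Background: "the reported diagnostic accuracy of EUS for gastrointestinal SELs is approximately 43%–79" per cent. Section 10.3 also plans a multivariable logistic regression for factors independently associated with concordance.

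**The concern.** For a continuous factor and two groups, one-way ANOVA is the two-sided t-test with a pooled variance. The pooled variance is weighted towards the larger group. If the smaller group is the more variable, the standard error is too small and the test rejects too often. If the larger group is the more variable, the standard error is too large and real differences are missed. With equal group sizes the two effects nearly cancel.

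In this study the outcome forms the groups, so balance cannot be arranged. Diameter is positive and may well be skewed (an assumption), in which case spread could differ between groups. Diameter is also an obvious candidate factor, and the primary objective in 2.1 is to identify factors associated with concordance. A univariable p-value for diameter with the wrong error rate would be reported against that objective.

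**Working it through.** **The plan's own figure.** Section 10.1 gives "effect size of 0.25", alpha 0.05, power 0.80, "10 predictors, and 2 groups", and concludes that "the required sample size was calculated to be 269 cases". Take 0.25 as Cohen's f and the noncentrality as λ = f²N. An F test with 10 numerator and N − 2 denominator degrees of freedom has power 0.798 at N = 268 and 0.8003 at N = 269, so 269 is reproduced. A one-way ANOVA on two groups has 1 numerator degree of freedom and needs N = 128 (power 0.801). So 269 is used below only as the planned number of cases.

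**Splits.** Background accuracy serves as a proxy for concordance: 0.43 × 269 = 115.7, giving 116:153, and 0.79 × 269 = 212.5, giving 213:56 (concordant:non-concordant).

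**Formula.** Let the concordant SD be 1 and the non-concordant SD be r, with sizes n₁ and n₂.

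- True variance of the mean difference: T = 1/n₁ + r²/n₂.
- Variance that ANOVA uses: P = s²(1/n₁ + 1/n₂), with s² = [(n₁ − 1) + (n₂ − 1)r²]/(n₁ + n₂ − 2).
- Large-sample type I error: 2[1 − Φ(1.96√(P/T))].

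**Worked cases.**

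- 213:56, r = 2: T = 1/213 + 4/56 = 0.0761. s² = (212 + 55 × 4)/267 = 1.618, so P = 1.618 × 0.02255 = 0.0365. P/T = 0.479; error 17.5%.
- 213:56, r = 0.5: T = 0.00916, P = 0.01907, P/T = 2.08; error 0.5%.
- 213:56, r = 1.25: T = 0.0326, P = 0.0252, P/T = 0.772; error 8.5%.
- 116:153, r = 0.5: T = 0.01025, P = 0.00869, P/T = 0.847; error 7.1%.

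**Simulation.** Type I error (%) of ordinary ANOVA at nominal 5%, with normal data, equal means and 200,000 replicates per cell. The ratio r is assumed throughout.

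| Split | r = 0.5 | 0.67 | 0.8 | 1 | 1.25 | 1.5 | 2 |
|---|---|---|---|---|---|---|---|
| 116:153 | 7.1 | 6.4 | 5.7 | 4.9 | 4.3 | 3.9 | 3.4 |
| 134:135 | 5.1 | 5.0 | 5.0 | 5.0 | 4.9 | 5.1 | 5.0 |
| 161:108 | 2.7 | 3.5 | 4.1 | 5.0 | 6.1 | 6.9 | 8.2 |
| 188:81 | 1.2 | 2.3 | 3.2 | 5.0 | 7.2 | 9.2 | 12.4 |
| 213:56 | 0.5 | 1.4 | 2.6 | 5.0 | 8.4 | 12.0 | 17.5 |

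Welch's test lies between 4.9% and 5.1% in all of these cells. In large samples the distortion depends on the split and the SD ratio, not on the total, so more cases would not remove it.

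**Cost of Welch when variances are equal.** With the mean difference set for about 80% power, the loss is 0 points from 43:57 to 60:40 (to the nearest tenth), 0.2 at 70:30 and 0.7 at 79:21 (79.8% to 79.1%). At 90:10, outside the Background range, it is 2.2 points.

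**Skewed data.** For lognormal data with equal arithmetic means at 213:56, and coefficients of variation 0.5 (concordant) and 1.0 (non-concordant), ordinary ANOVA rejects in 17.4% and Welch in 7.6%. With the coefficients exchanged the rates are 1.0% and 5.0%.

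**The case against.** The strongest reply is that the large figures sit in one corner. They need both the 79% end of an accuracy range reported for gastrointestinal lesions in general and a twofold SD ratio that no document supports. For age there is no particular reason to expect different SDs. This stands. A reader might infer that the error rate generally runs from under 1% to about 17%. The documents do not support that: at 43% concordance a twofold ratio gives 3.4% to 7.1%, and near 50:50, which lies inside the range, about 5%. Nor is the non-concordant group always the smaller one. At 116:153 it is the larger, and the direction of the distortion reverses.

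A second reply is that the consequence is limited. This also stands. Logistic regression makes no equal-variance assumption, and the plan does not say that ANOVA results choose the variables for it. A reader might also infer that the sample size rests on this test because 10.1 names it, but 269 is not the number that a two-group one-way ANOVA requires.

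A third reply is that Welch is neither entirely free nor a full remedy for skew. That is correct: the loss reaches 0.7 points at 79:21, and the lognormal example leaves 7.6%. Log-transforming diameter might seem the natural completion, but it changes the question. When arithmetic means are equal and spreads differ, geometric means do differ. Under such lognormal data at 213:56 (log-SD 0.5 in the concordant group, SD ratios 0.5 to 2), Welch on the log scale rejects in roughly 20% to 54% of samples.

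None of these replies gives a reason to prefer the pooled test. Within the Background range Welch costs less than one power point and is never materially worse.

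**Conclusion.** The point holds as a minor, inexpensive improvement. Sections 10.1 and 10.3 name only the equal-variance test, for groups whose sizes are not controlled. At 79% concordance a twofold SD difference moves the 5% level to about 0.5% or 17.5%. A 1.25-fold difference moves it to about 8.4% if the smaller group is the more variable, or 2.6% if the larger is. At 43% a twofold difference gives 3.4% to 7.1%, and near equal groups the effect is negligible. These figures rest on assumed SD ratios, on the Background accuracy as a proxy for concordance, and on 269 cases.

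The effect is confined to the univariable comparisons of age and maximum diameter. It is no ground for doubting the logistic regression.

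**What to change.** In 10.3, specify Welch's test in place of ordinary one-way ANOVA for the continuous factors, and report the mean difference between groups with its unequal-variance 95% CI. Make the wording in 10.1 agree. Choose the test in advance, not after inspecting the variances.

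Log-transforming maximum diameter is optional. If it is used, the plan should say that the comparison is then of geometric means and report their ratio with its 95% CI. If it is not used, the plan should acknowledge that Welch is only approximate for strongly skewed diameter.

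The cost is one phrase. Welch is an option in the same SPSS one-way procedure, and no new data or cases are needed. The power loss is under one point across the 43% to 79% range when variances are equal.
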